7.2.3. Clinical laboratory evaluations

Blood and urine samples will be collected for clinical laboratory evaluations at the times indicated in the Schedule of Assessments in [Appendix 5](#). Clinical laboratory evaluations are listed in [Appendix 2](#). Additional clinical laboratory evaluations will be performed at other times

if judged to be clinically appropriate or if the ongoing review of the data suggests a more detailed assessment of clinical laboratory safety evaluations is required.

Serum pregnancy test is to be performed in female patients of child bearing potential at a local (site) laboratory, during screening or Day 1, discharge, and ET/EOT. A urine pregnancy test may be performed but must be confirmed with a serum pregnancy test (screening only). The Follow-up/EOS visit test will be a urine pregnancy test only (no serum pregnancy test confirmation). Additionally, local/country regulations will be followed as applicable (eg., a pregnancy test one month following the last dose of study treatment in female patients of childbearing potential).

Screening laboratory test will be assessed by a local laboratory, and baseline and postbaseline laboratory tests will be assessed by a central laboratory. If delays in transportation of the samples are encountered, then local safety laboratory samples can be obtained instead for samples that can't be frozen for shipment (e.g. hematology and urine). Baseline laboratory tests can be done once patients eligibility is confirmed. The investigator will perform a clinical assessment of all clinical laboratory data.

All screening laboratory results must be available and reviewed before the patient receives the first dose of study treatment on Day 1. After the test results are evaluated, the investigator should judge whether the patient is still eligible to stay in the study. Significant abnormal values occurring during the study will be followed until repeat test results return to normal, stabilize, or are no longer clinically significant.

In this study, clinical laboratory tests will be performed predose on Days 1, 5, and 14 (+2 days).

7.2.4. Vital signs, physical examination, and other safety evaluations

7.2.4.1. *Physical examinations*

Patients will be examined at the times indicated in the Schedule of Assessments in [Appendix 5](#). A complete physical examination including general appearance, HEENT, lymphatic, cardiovascular, respiratory, gastrointestinal, musculoskeletal, neurological, and dermatological systems will be performed at screening.

7.2.4.2. *Vital signs*

Seated blood pressure, seated pulse rate, respiratory rate, and body temperature will be assessed for safety and efficacy endpoints at the times indicated in the Schedule of Assessments in [Appendix 5](#). Vital signs may also be performed at other times if judged to be clinically appropriate or if the ongoing review of the data suggests a more detailed assessment of vital signs is required.

All measurements will be performed singly and repeated once if outside the relevant clinical reference range. Patients must be seated for at least 5 minutes before blood pressure and pulse rate measurements. Body temperature will be measured according to site's local practices and may include oral, tympanic, rectal, axillary, or frontal.

Pulse oximetry to measure the peripheral capillary oxygen saturation (SpO₂) will be collected in the eCRF during the study. SpO₂ measurements should be collected at Screening, Day 1, Day 3, Day 5, Day 7, Day 14/EOT or Discharge/ET, and Day 28 visits if patient is in hospital (refer to [Appendix 5](#)). For discharged patients, SpO₂ should be collected at Day 5 and Day 14 if visits completed in clinic/hospital. SpO₂ may be collected if the visit is conducted at home by a home health service professional, but is not required.

Fraction of inspired oxygen (FiO₂) data will be collected and partial pressure of oxygen (PaO₂) will also be collected if done as standard of care as per [Appendix 5](#).

7.2.4.3. *12-lead Electrocardiogram Parameters*

Single 12-lead ECGs will be recorded after the patient has been supine and at rest for at least 5 minutes at screening and after screening as per [Appendix 5](#). The evaluation items for all ECGs will include heart rate, QRS complex, QT interval, QT interval corrected for heart rate, and RR interval. At screening, the investigator should examine the ECG for signs of cardiac disease that could exclude the patient from the study. An assessment of normal, abnormal and not clinically significant, or abnormal and clinically significant will be performed by the investigator. If the ECG is considered abnormal, the abnormality will be documented on the eCRF.

Additional 12-lead ECGs may be performed at other times if judged to be clinically appropriate or if the ongoing review of the data suggests a more detailed assessment of ECGs is required.

7.2.4.4. *Chest imaging*

A chest x-ray or CT scan will be performed at the times indicated in the Schedule of Assessments in [Appendix 5](#).

7.3. Pharmacokinetic Assessment

The PK evaluation of antroquinonol in patients in the sentinel cohort includes C_{trough}, C_{max}, t_{max}, AUC_{0-1ast}, and AUC_{tau}.

Blood samples for PK evaluations will be on Day 3 at predose and 1, 2, 3, 4, 6, 8, and 12 hours postdose (after the first study drug dose of the day), for hospitalized patients only. For discharged patients/outpatient visits, the 12-hour sample can be omitted for scheduling purposes.

On Day 14 if patients are still hospitalized, predose and 2 hours postdose samples (after the first study drug dose of the day) will also be collected.

Patients who are discharged from the hospital on Day 2 prior to PK sampling will not need to return to the clinic for sample collection.

The PK samples will not be collected for the expansion cohort.

8. SAMPLE SIZE AND DATA ANALYSES

8.1. Determination of sample size

The decision to include 20 patients in the sentinel cohort was chosen arbitrarily.

The sample size for the expansion group has been determined to provide evidence of proof of concept efficacy should the treatment prove effective. The primary endpoint and futility rules are based on assessments at Day 14 to enable rapid decision making, and the assessment at Day 28 will also be presented as a secondary endpoint.

The detailed assumptions are as follows, and the calculations include the patients from the sentinel cohort that were treated with the same dose used for the expansion cohort:

Alpha	0.2 (one-sided)
Power	80%
Drop-Outs assumed	2%
Endpoint	Odds of patient alive and respiratory failure free by Day 14
Effect Size	78% Placebo 89% Antroquinonol
Futility boundary shape	Manually chosen. Odds Ratio of 3.5 at interim analysis 1 in favor of placebo, and 1.2 at interim analysis 2 in favor of placebo. Equivalent to 4 patients not in respiratory failure on antroquinonol vs 7 on placebo at interim analysis 1, or 26 patients not in respiratory failure on antroquinonol vs 28 on placebo at interim analysis 2. Nonbinding
Efficacy boundary shape	None

In addition, the performance of the study under the following scenarios for the efficacy of antroquinonol were also considered:

Antroquinonol harmful	78% Placebo 67% Antroquinonol
Antroquinonol no effect	78% Placebo 78% Antroquinonol

The nonbinding decision rules of the interim analysis and stopping probabilities under:

Look #	Sample Size	Futility Stopping Boundary Odds Ratio	Cumulative Futility Stopping Probability		
			Drug harmful	No effect	Drug effective
Interim analysis 1	20	3.5	25%	17%	5%
Interim analysis 2	80	1.2	79%	44%	9%
Final	174	0.697			

The decision rules may be modified pending discussion with the DMC, but any modifications will still be considered nonbinding; therefore, no adjustment for the final alpha will be made.

The estimates of the probabilities of response are supported by recently published analysis by Richardson et al ¹⁹, which reported 21% mortality of hospitalized patients, and 320 patients requiring ventilation. The authors reported 88.1% mortality for patients requiring ventilation, implying that 282 patients died after receiving ventilation. Since 553 patients died overall, this means that 271 patients died without receiving mechanical ventilation, and therefore $320+271 = 591$ patients either died or received mechanical ventilation. This leads to the conclusion that $591/2634$ (22.4%) patients, either died or received mechanical ventilation at some point.

It is anticipated that at least 50% of patients will need to benefit from antroquinonol to be considered a clinical breakthrough, hence an improvement from 22% to 11% is considered appropriate for the alternative hypothesis.

8.2. Analysis Populations

The following analysis populations will be included for this study:

Intention-to-treat (ITT): All randomized patients. Patients will be analyzed according to the treatment to which they were randomized.

modified ITT (mITT): All randomized patients who received at least 1 dose of study drug.

Per Protocol Set (PPS): All patients from the ITT set who have no important protocol deviations during the study. Patients with any important protocol deviations shall be excluded from the PPS prior to database lock.

Safety Set (SS): All patients who have received at least 1 dose of the study treatment. Patients will be analyzed according to the study treatment they actually received.

Pharmacokinetic Set (PKS): Patients in the sentinel cohort who have received at least 1 dose of the study treatment and have at least 1 evaluable plasma concentration without important protocol deviations or events thought to significantly affect the PK.

The ITT set will be the primary analysis population for efficacy and the mITT and PPS will be the supportive analysis populations for efficacy analysis. Safety endpoints will be analyzed using the SS. The PKS will be used for PK assessment.

8.3. General Considerations

Continuous variables will be summarized by the standard descriptive statistics: number of patients (n), mean, standard deviation, median, minimum, and maximum. Frequency of patients or events and percentages will be summarized in categorical variables.

Missing values on clinical improvement score will be imputed using Last Observation Carried Forward for a maximum of 1 day at Day 7, 2 days at Day 14, and 4 days at Day 28. For

respiratory failure status, where a patient has died, their status will not be considered missing but will be treated as an observation at each timepoint.

Unless otherwise stated, all regression models will be adjusted for age and remdesivir or other authorized treatments for COVID-19 use at baseline.

Results will be considered statistically significant at one-sided alpha of 0.025, and considered to indicate promising trend at one-sided alpha of 0.2.

Additional information is available in the statistical analysis plan (SAP).

8.4. Efficacy Analysis

The efficacy analysis will be based on the final SAP.

8.4.1. Primary efficacy outcome measures

The proportion of patients from each treatment group who are alive and free of respiratory failure on Day 14 will be compared using logistic regression. The p-value will be based on the Wald test. The primary model will be stratified by remdesivir or other authorized treatments for COVID-19 use at baseline and by age at baseline (> 65 years vs ≤ 65 years).

8.4.2. Secondary efficacy outcome measures

Clinical improvement measured as a score on the WHO COVID-19 Clinical Improvement Ordinal Scale will be analyzed at each timepoint, adjusted for the clinical improvement score at baseline, age at baseline, and remdesivir or other authorized treatments for COVID-19 use at baseline, using an ordinal logistic regression on Days 7, 14, and 28. In addition, descriptive statistics will be provided for average score, and the proportion of patients at or below each score, at each timepoint. Time to 2-point improvement from baseline in WHO COVID-19 Clinical Improvement score, time to score of 2 or lower, and time to score of 0, will also be analyzed.

The hazard ratio and its 95% confidence interval for time to event outcomes will be estimated by Cox proportional hazard model, with patients censored at the time they are provided any antiviral therapy not prescribed at baseline, or on Day 28 if they have not yet recovered. Patients who die at any time will be considered not yet recovered by Day 28. Median time to 2-point improvement, time to score of 2 or lower, and time to score of 0 will be estimated by Kaplan-Meier (KM) method, and the KM curve will be provided. The p-value for comparison between groups will be obtained based on proportional hazards modeling stratified by the same covariates as the primary model.

Duration of hospitalization and ICU stay up to Day 28 will be analyzed using normal regression, using the same covariates as for the primary endpoint. Patients who die will be considered as continuing to require hospitalization or ICU stay up to Day 28 for the purposes of this analysis.

Time to virological clearance, measured as study days from start of treatment to first negative SARS-CoV-2 PCR test, will be evaluated using similar statistical methods as clinical

improvement. All patients who have died will be considered as not having cleared the virus by Day 28

Rate of change in viral load will be summarized descriptively and estimated using a Mixed Model for Repeated Measurements model. The model will include the treatment group, age, remdesivir or other authorized treatments for COVID-19 use at baseline, visit, and the interaction between visit and the treatment group as fixed factors, and will include the baseline value as a covariate. If a patient has tested negative, they are assumed to be negative until they are tested again.

Proportion of patients with vital status of death in both groups on Days 7, 14, and 28 will be compared using logistic regression stratified by the same covariates as the primary model.

Proportion of patients alive and free of respiratory failure on Days 7 and 28 will be compared using the same analysis as the primary endpoint.

COVID-19 symptoms at screening and on Days 7, 14, and 28 will be summarized, and compared using logistic regression following the same method as the primary endpoint.

8.4.3. Exploratory outcome measures

Subgroup analyses will be provided for the parameters of age, sex, and remdesivir or other authorized treatments for COVID-19 use at baseline. Investigation of the interaction between these parameters and the treatment effect will be provided.

The impact on efficacy of any new authorized treatments recommended as SoC for COVID-19 during the course of the study will also be evaluated.

8.5. Safety Analysis

Safety variables include incidence of AEs (or TEAEs), laboratory test results, vital signs, and complete physical examination, ECG, and chest imaging (x-ray or CT scan) findings. All safety analyses will be based on the SS. No formal statistical analysis of the safety data will be performed.

Adverse events will be coded according to MedDRA, version 23.0 dated 19 April 2020 (exclusively meant for COVID-19) or later.

The number and percentage of patients with TEAEs, SAEs, TEAEs related to study treatment, SAEs related to study treatment, TEAEs leading to treatment discontinuation, TEAEs leading to study discontinuation, and TEAEs leading to death will be summarized by SOC, PT, and treatment group. In addition, the severity of TEAEs and relationship to study treatment will be summarized by SOC, PT, and treatment group.

The AE summary tables will include counts of patients. Therefore, if a patient experiences more than 1 episode of a particular AE, the patient will be counted only once for that event. If a patient has more than one AE that is coded to the same PT, the patient will be counted only once for that

PT. Similarly, if a patient has more than 1 AE within an SOC, the patient will be counted only once in that SOC.

Test values and change from baseline will be summarized descriptively for specific laboratory test results, vital signs, complete physical examination results, ECG findings, and chest imaging (x-ray or CT scan) findings. Where applicable, shift tabulations by treatment group will be presented.

Pregnancy test results and patients with confirmed positive pregnancy test result will be listed.

8.6. Pharmacokinetic Analysis

Descriptive statistics will be provided for antroquinonol plasma concentrations at prespecified timepoints and derived PK parameters (listed in [Section 7.3](#)).

8.7. Interim Analysis

The following interim analyses will be conducted:

- Interim analysis 1, for safety and futility, will be conducted when the sentinel cohort has completed at least 14 days of treatment. Enrollment will be paused once the 20th patient in the sentinel cohort has been enrolled and started treatment until the results of the interim analysis are known.
- Interim analysis 2, for safety and futility, will be conducted on all data collected up to the 80th randomized patient completing 14 days of treatment. Enrollment may be restricted at the 100th patient until the DMC has completed the assessment to prevent excessive enrollment.

All interim analyses will be reviewed by the unblinded DMC. The DMC will not make recommendations to stop the study early for efficacy. Futility rules provided to the DMC will be nonbinding, and therefore no adjustment of the final analysis will be made. Should either ≥ 2 patients experience treatment related SAEs or severe AEs that are of a similar nature at any time, enrollment will be paused while the DMC reviews safety data.

A [DMC Charter](#), which includes detailed processes, will be prepared.

10. APPENDICES

Appendix 1. Adverse Event Definitions

Definitions

An adverse event (AE) is any untoward medical occurrence associated with the use of a drug in humans, whether or not considered drug related. This includes the following:

- Any clinically significant worsening of a pre-existing condition.
- Any recurrence of a pre-existing condition.
- An AE occurring from overdose of a sponsor study drug whether accidental or intentional (ie, a dose higher than that prescribed by a health care professional for clinical reasons).
- An AE occurring from abuse of a sponsor study drug (ie, use for nonclinical reasons).
- An AE that has been associated with the discontinuation of the use of a sponsor study drug.
- Clinically significant laboratory abnormalities (i.e. the laboratory abnormality is associated with symptoms, requires medical intervention, or requires changes to study drug treatment).

Note: A procedure is not an AE, but the reason for a procedure may be an AE.

A pre-existing condition is a clinical condition (including a condition being treated) that is diagnosed before the patient signs the informed consent form and that is documented as part of the patient's medical history.

The questions concerning whether the condition existed before the start of the active phase of the study and whether it has increased in severity and/or frequency will be used to determine whether an event is a treatment-emergent AE. An AE is considered to be treatment-emergent if (1) it is not present when the active phase of the study begins and is not a chronic condition that is part of the patient's medical history, or (2) it is present at the start of the active phase of the study or as part of the patient's medical history, but the severity or frequency increases during the active phase. The active phase of the study begins at the time of the first dose of the study drug. The active phase of the study ends at the Day 28 Follow-up/End of Study (EOS) visit.

Disease-specific signs and symptoms that were ongoing prior to study entry will not be considered AEs unless they worsen (eg, increase in frequency or severity) unexpectedly during the course of the trial.

Reporting of Adverse Events

At each visit the investigator, or delegate, will determine whether or not any AEs have occurred. Nonleading questions such as "How are you feeling today?" or "Have you had any health concerns since your last visit?" should be used to elicit the patient to report any possible AEs. If any AEs have occurred, they will be recorded in the AE section of the electronic case report form (eCRF) and in the patient's source documents. If known, the diagnosis should be recorded, in preference to listing the individual signs and symptoms.

Adverse event reporting begins from the time of informed consent and ends 2 weeks after the last dose of study treatment (Day 28 ± 2 days).

Assessment of Severity

The investigator will be asked to provide an assessment of the severity of the AE using the following categories:

- **Mild:** Usually transient and may require only minimal treatment or therapeutic intervention. The event does not generally interfere with usual activities of daily living.
- **Moderate:** Usually alleviated with additional specific therapeutic intervention. The event interferes with usual activities of daily living, causing discomfort but poses no significant or permanent risk of harm to the patient.
- **Severe:** Interrupts usual activities of daily living, significantly affects clinical status, or may require intensive therapeutic intervention.

Relationship to Study Treatment

The investigator will make a determination of the relationship of the AE to the study drug using a 4-category system according to the following guidelines:

- **Not related:** When the AE is definitely caused by the patient's clinical state, or the study procedure/conditions.
- **Unlikely Related:** When the temporal association between the AE and the drug is such that the drug is not likely to have any reasonable association with the AE.
- **Possibly Related:** When the AE follows a reasonable temporal sequence from the time of drug administration but could have been produced by the patient's clinical state or the study procedures/conditions.
- **Related:** When the AE follows a reasonable temporal sequence from administration of the drug, abates upon discontinuation of the drug, and follows a known or hypothesized cause-effect relationship.
- If causality is assessed as Related or Possibly Related, the event will be considered as related for regulatory reporting purposes.

Action Taken for Adverse Events

The investigator or designee will record the action taken for the AE in the eCRF. Actions taken will include:

- **Dose not changed:** The medication schedule was not changed.
- **Drug withdrawn:** The medication schedule was modified through termination of the prescribed regimen of medication.
- Not applicable
- Unknown.

Follow-up of Adverse Events

All (S)AEs that are ongoing at the time of discontinuation, or that develop prior to the final Follow-up/EOS visit, will be followed for up to 30 days following the last dose of study treatment, or until resolution or stabilization.

Adverse Drug Reactions

All noxious and unintended responses to an investigational medicinal product (IMP; ie, where a causal relationship between an IMP and an AE is at least a reasonable possibility) related to any dose should be considered adverse drug reactions (ADRs).

For marketed medicinal products, a response to a drug which is noxious and unintended and which occurs at doses normally used in man for prophylaxis, diagnosis, or therapy of diseases or for modification of physiological function, is to be considered an ADR.

An unexpected ADR is defined as an adverse reaction, the nature or severity of which is not consistent with the applicable product information (eg, investigator's brochure for an unapproved IMP).

Serious Adverse Events

An SAE is any AE occurring at any dose that meets 1 or more of the following criteria:

- Results in death
- Is life-threatening (see [below](#))
- Requires patient hospitalization or prolongation of an existing hospitalization (see [below](#))
- Results in a persistent or significant disability or incapacity (see [below](#))
- Results in a congenital anomaly or birth defect.

Additionally, important medical events that may not result in death, be life-threatening, or require hospitalization may be considered SAEs when, based on appropriate medical judgment, they may jeopardize the patient and may require medical or surgical intervention to prevent one of the outcomes listed above. Examples of such events include allergic bronchospasm requiring intensive treatment in an emergency room or at home, blood dyscrasias or convulsions that do not require hospitalization, or development of drug dependency or drug abuse.

A ***life-threatening adverse event*** is any AE that places the patient at immediate risk of death from the event as it occurred. A life-threatening event does not include an event that might have caused death had it occurred in a more severe form but that did not create an immediate risk of death as it actually occurred. For example, drug-induced hepatitis that resolved without evidence of hepatic failure would not be considered life-threatening, even though drug-induced hepatitis of a more severe nature can be fatal.

Hospitalization or prolongation of a hospitalization is a criterion for considering an AE to be serious. Hospitalization is to be considered only as an overnight admission. In the absence of an AE, the participating investigator should not report hospitalization or prolongation of hospitalization. This is the case in the following situations:

- Hospitalization or prolongation of hospitalization is needed for a procedure required by the protocol (excluding hospitalization required by the index case). Day or night survey visits for biopsy or surgery required by the protocol are not considered serious.
- Hospitalization or prolongation of hospitalization is part of a routine procedure followed by the study center (eg, stent removal after surgery). This should be recorded in the study file.
- Hospitalization for survey visits or annual physicals fall in the same category.

In addition, a hospitalization planned before the start of the study for a pre-existing condition that has not worsened does not constitute an SAE (eg, elective hospitalization for a total knee replacement due to a pre-existing condition of osteoarthritis of the knee that has not worsened during the study).

Disability is defined as a substantial disruption in a person's ability to conduct normal life functions (ie, the AE resulted in a significant, persistent, or permanent change, impairment, damage, or disruption in the patient's bodily function/structure, physical activities, or quality of life).

If there is any doubt as to whether a case constitutes an AE or SAE based on the information available, the case should be treated as an SAE.

Pregnancy

The investigator will collect pregnancy information on any female patient who becomes pregnant while participating in this study. Information will be recorded on the appropriate form and submitted to the sponsor (or designee) within 24 hours of learning of a patient's pregnancy. The patient will be followed to determine the outcome of the pregnancy.

The investigator will attempt to collect pregnancy information on any male patient's female partner who becomes pregnant while the male patient is in this study. After obtaining the necessary signed informed consent from the pregnant female partner directly, the investigator will record pregnancy information on the appropriate form and submit it to the sponsor (or designee) within 24 hours of learning of the partner's pregnancy. The female partner will also be followed to determine the outcome of the pregnancy.

Information on the status of the mother and child will be forwarded to the sponsor (or designee). Generally, the follow-up will be no longer than 6 to 8 weeks following the estimated delivery date. Any termination of the pregnancy will be reported regardless of fetal status (presence or absence of anomalies) or indication for the procedure.

While pregnancy itself is not considered to be an AE or SAE, any pregnancy complication or elective termination of a pregnancy will be reported as an AE or SAE. A spontaneous abortion is always considered to be an SAE and will be reported as such. Any poststudy pregnancy-related SAE considered reasonably related to the IMP by the investigator will be reported to the sponsor. While the investigator is not obligated to actively seek this information in former study patients, he or she may learn of an SAE through spontaneous reporting.

Events not to be reported as adverse events

A lack of drug effect is not an AE in this study because the purpose of the clinical study is to establish treatment effect.

The following study-specific clinical events related to Coronavirus Disease 2019 (COVID-19) are exempt from AE reporting unless the investigator judges the event to be related to study drug:

- Hypoxemia due to COVID-19 requiring non-invasive ventilation or high flow oxygen;
- Respiratory failure due to COVID-19 requiring invasive mechanical ventilation or extracorporeal membrane oxygenation

Any clinically significant abnormal laboratory findings or other abnormal safety assessments which are associated with the underlying disease under study, unless judged by the investigator to be more severe than expected for the participant's condition.

The disease being studied or expected progression, signs, or symptoms of the disease being studied, unless more severe than expected for the participant's condition.

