### 7.7.2 Adverse Events

All adverse events (AEs) recorded on the eCRF will be coded using the MedDRA dictionary [Version 23.0 dated 19 Apr 2020 or a later version if updated during the study (exclusively meant for COVID-19)] and classified as either pre-treatment AEs or treatment – emergent AEs (TEAEs) as follows:

- Pre-treatment AEs are events that start after the signing the informed consent form and prior to the date of first dose of study treatment.
- TEAEs are events with start date on or after the date of first dose of study treatment and up to 2 weeks after date of last dose of study treatment or events with start date prior to the date of first dose of study treatment whose severity worsens on or after the date of first dose of study treatment.

If an AE can't be classified as pre-treatment AE or TEAE due to missing/partial dates, it will be classified as TEAE.

The number and percentage of patients reporting each pre-treatment AE will be summarized for each treatment group and overall, by System Organ Class (SOC) and Preferred Term (PT) for SS.

All AE data will be listed by treatment group and overall. Treatment-emergence status will be flagged in the listing. In addition, corresponding listings of serious AEs (SAEs), treatment-related AEs, AEs leading to discontinuation of study treatment, AEs leading to discontinuation of study and AEs resulting in death will be produced for the SS.

The severity of all AEs is recorded as mild, moderate, or severe. If severity is missing for a TEAE, it will be considered severe only in the overall category in the summary tables.

The relationship between an AE and treatment is assessed as related, possibly related, unlikely related, or not related. A treatment-related AE is an AE considered by the investigator as related or possibly related to treatment or with missing relationship to treatment.

An overview table will summarize the number and percentage of patients with at least one of the following TEAEs, along with the number of corresponding TEAEs, where

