## 8. Changes in Planned Analysis

No changes on statistical analysis methods from the protocol.

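### SAP 7.7.2 omits the protocol's frequency criterion, so an AE dated before first dose that worsens only in frequency is a TEAE under the protocol but not in the SAP

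*Protocol*

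**What the plan says.** **Protocol, Appendix 1 (Adverse Event Definitions).** Treatment emergence turns on whether a condition was there before the active phase and whether it has "increased in severity and/or frequency will be used to determine whether an event is a treatment-emergent AE". The rule then has two limbs. The second covers an event where "it is present at the start of the active phase of the study or as part of the patient's medical history". It makes such an event treatment-emergent if it worsens in either respect: "but the severity or frequency increases during the active phase". The reference point is first dose: "The active phase of the study begins at the time of the first dose of the study drug". Frequency appears again for COVID-19 signs and symptoms already ongoing at entry, which are not AEs "unless they worsen (eg, increase in frequency or severity) unexpectedly during the course of the trial".

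**SAP, section 7.7.2 (Adverse Events).** The first limb takes events that start from the date of first dose up to 2 weeks after the last dose. The second limb takes "events with start date prior to the date of first dose of study treatment whose severity worsens" from first dose onward. Frequency is not mentioned. The only default to TEAE is for an AE whose dates are too incomplete to classify it.

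**SAP, section 8 (Changes in Planned Analysis).** "No changes on statistical analysis methods from the protocol".

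**The concern.** The protocol names frequency three times in Appendix 1, and the SAP leaves it out of the rule that will be programmed. Severity is recorded in three classes (mild, moderate, severe), defined by interference with daily activities, need for treatment and clinical impact. A symptom can occur more often without crossing from one class to the next. Under the SAP such an event, if it keeps its start date from before first dose, does not count as treatment-emergent.

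Protocol 8.5 builds the safety summaries on TEAEs, and the SAP's overview table counts TEAEs. What is at stake is whether those tables follow the definition the protocol set. Because SAP section 8 reports no change, a reader of the study report would not know that a narrower definition had been used.

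**Working it through.** The plan gives no figure on this point and no rate enters the argument, so there is nothing to recompute. The check is to apply each definition to the same kinds of record.

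| Record | Protocol Appendix 1 | SAP 7.7.2 |
|---|---|---|
| (a) Starts after consent and before first dose; more frequent on treatment, same severity class; one record with the original date | TEAE (frequency increased) | Pre-treatment AE, not a TEAE |
| (b) Starts before consent or is in the medical history; more frequent on treatment, same class; recorded with the original date | TEAE | Neither a TEAE nor a pre-treatment AE, since that class requires a start after consent |
| (c) Starts before first dose; severity class rises on treatment | TEAE | TEAE |
| (d) Increase in frequency on treatment entered as a new record dated on or after first dose, within the SAP's window | TEAE | TEAE (by start date) |

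The two definitions disagree in (a) and (b) and agree in (c) and (d). The SAP's default for incomplete dates does not rescue (a) or (b), because their dates are known.

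How often can (a) and (b) arise?

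- Case (a) needs an AE that starts in the screening period (planned at up to 3 days), is still present at first dose, worsens in frequency only, and stays on one record.
- Case (b) needs an AE record dated before consent. Appendix 1 starts AE reporting at consent. It makes the clinically significant worsening of a pre-existing condition the AE, not the condition itself, and treats ongoing disease symptoms in the same way. The natural start date of such an AE is the date of worsening, which turns (b) into (d). Nothing in the documents tells sites to date the worsening back to the original onset.

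Case (a) is therefore the main route. Neither document gives a rate for it.

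**The case against.** The strongest reply is that the wording differs but little follows from it.

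- For conditions present before consent, the protocol's own AE definition makes the worsening the event, so the SAP's first limb should capture it. This stands, and it confines the problem mainly to the screening window.
- Any loss depends on how sites date a worsening. The eCRF and its completion instructions are not part of the documents. This also stands, but it means that classification rests on site practice, which is a reason to settle the rule.
- Severity is a recorded field, and the documents describe no frequency field for AEs. Adding a word to the SAP may not be programmable by itself. This is right, and it shapes the fix.
- The events are not hidden. SAP 7.7.2 summarises pre-treatment AEs by SOC and PT for each group, and lists all AEs with a treatment-emergence flag. This stands: the loss is from the TEAE tables, not from the report.

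A reader might go further and infer that the rule hides gastrointestinal toxicity on active treatment, perhaps in several patients per arm. Protocol 1.2.3 reports diarrhoea in 32.2%, nausea in 6.7% and vomiting in 4.4% on antroquinonol in the hyperlipidemia study. The documents do not support that inference, for three reasons:

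- Those figures are on-treatment incidences from once-daily dosing over 12 weeks. They do not give the share of patients who enter with a symptom that then becomes more frequent.
- Exclusion criterion 15 bars diarrhea at baseline, so the drug's commonest event should rarely be present at first dose. SAP 7.4 does tabulate patients with diarrhea at baseline, so some may occur. Nausea and vomiting as such are not named in that criterion.
- The same rule applies to both blinded arms, and SAP 7.7.2 plans no statistical comparison of AEs between them. A loss falling mainly on one arm is possible if the drug raises symptom frequency, but nothing in the documents shows it.

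What the reply does not remove is that the two definitions differ and SAP section 8 says they do not.

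**Conclusion.** The discrepancy holds. An AE that starts before first dose, becomes more frequent on treatment within its severity class and keeps its original start date is a TEAE under Protocol Appendix 1 and is left out of the SAP's TEAE tables. The departure is not declared. The event remains in the AE listing and, if it began after consent, in the pre-treatment AE summary.

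The number affected is probably small and cannot be estimated from the documents. No direction of bias between arms is established, and no efficacy analysis is touched.

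This rests on two assumptions. First, some sites may keep a worsening AE on its original record, which the documents neither require nor forbid. Second, the SAP's tables by SOC and PT, which are worded as AE tables, are meant to be TEAE tables, as Protocol 8.5 asks.

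**What to change.** 1. In SAP 7.7.2, insert *or frequency* after *severity* in the second limb of the TEAE definition, so that it matches Protocol Appendix 1.
2. Because the documents describe no frequency field for AEs, add a line to the eCRF completion instructions: any worsening in severity or frequency after first dose is entered as a new AE record dated at the worsening. The existing date-based limb of the SAP definition then captures it.
3. Before database lock, check under the blind any records already entered with a start date before first dose that were ongoing at first dose.
4. If the sponsor wants severity only, keep the SAP wording and declare the departure from Appendix 1 in SAP section 8.

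The cost is one phrase in the SAP, one line of site instruction and a short blinded data check. The downside is that TEAE counts may rise slightly in both arms.
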